	
95% confidence intervals will be calculated. Statistical procedures to check on a normal distribution of data, to be applied in case of non-normally distributed data, and to verify and handle minimization factors will be described in the statistical analysis plan, which will be finalized prior to unblinding.
 
2. 28-day mortality (all cause death) The percentage of patients who have died at day 28 will be presented by treatment group. Patients who will be discharged from hospital or early terminated before Day 28 will be considered having an event on the day of discharge or early termination, if a telephone interview was not possible and/or no information about alive/death status is known. The Chi-squared or Fisher's exact test will be used to compare proportions. 95% CIs will be additionally calculated. Logistic regression analyses will be conducted considering additional co-factors (will be detailed in the statistical analysis plan).3. Ventilator-free days (VFD) up to 28 days or hospital discharge VFD will be analyzed for both all patients as well as for the subgroup of patients who were alive at day 28 or hospital discharge. For the analysis of all patients separate analyses will be conducted for patients who died: a) VFD will be set to 0, b) the observed VFD until death will be considered. Summary tables will be generated the VFD will be compared using Wilcoxon rank sum test. In addition, bootstrap methods will be applied to calculate 95% confidence intervals and two-sided p-values for the difference in means.4. Proportion of responders, defined as ≥ 2 improvement in WHO's 11-Point Score system at day 7, 10, 14 and 28 Similar analyses as for 28-day mortality will be conducted.5. Time to death (all cause) will be analyzed using Kaplan-Meier estimates and plots, log-rank test, and Cox proportional hazards model (adjusted for minimization factors to derive hazard ratios and corresponding 95% confidence intervals). Patients who will be alive at day 28, or who will be discharged from hospital before day 28 will be censored at discharge if they cannot be reached at or after day 28 by means of a telephone interview. Further details will be described in the statistical analysis plan.6. Proportion of patients with any use of invasive mechanical ventilation up to 28 days or hospital discharge. Similar analyses as for 28-day mortality will be conducted.7. Time to first use of invasive mechanical ventilation up to 28 days or hospital discharge. Similar analyses as for time to death will be conducted.8. Absolute values and absolute change in P/F ratio over time The PF ratio is defined as PaO₂ [mmHg] divided by FiO₂ [%] and will be evaluated on each visit. Summary statistics for the PF ratio for both the absolute values and the absolute change from Baseline (day 1) will be tabulated.9. Absolute values and absolute change in the modified Sequential organ failure assessment score (mSOFA score) over time Similar analyses as for the PF ratio will be conducted.

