⁴ Vital signs include temperature, heart rate, respiration, blood pressure, and oxygen saturation. Vital signs need to be tested before and after each dose (within 30 min before/after IMP administration).

⁵ physical examination could also be documented in the context of the general visit/health status assessment e.g. during a general clinical review

⁶ Pregnancy Test: for FOCP only

⁷ Laboratory tests include the following: in case a local lab cannot perform any of these parameters it should be reported as missing value

- Inflammatory indicators: C- reactive protein (CRP), erythrocyte sedimentation rate (ESR), and procalcitonin.
- Blood routines include: red blood cell (RBC) count, hematocrit (HCT) or hematocrit total, and classification of white blood cells (WBC), hemoglobin (Hb), platelet (PLT) count.
- Urine routine includes: glucose (GLU), pH (PH), urinary protein (PRO), red blood cells (BLD), and white blood cells (LEU).
- Stool routine + occult blood: red blood cells (BLD), white blood cells (LEU), occult blood.
- Blood biochemistry includes: aspartate aminotransferase (AST), alanine aminotransferase (ALT), alkaline phosphatase (AKP), total bilirubin (TBI), total protein (ALB), albumin (ALB), urea nitrogen (BUN), Creatinine (Cr), uric acid (UA), potassium (K), sodium (Na), eGFR (assessment is calculated according to the formula used in local laboratory).
- Myocardial enzymes: creatine kinase (CK) and isoenzyme (CKMB), lactate dehydrogenase (of LDH), [alpha] - hydroxybutyrate dehydrogenase ([alpha] - HBD), troponin (of cTnI).
- Coagulation functions include: prothrombin time (PT), activated partial thromboplastin time (APTT), D- dimer, FIB

⁸ results do not need to be available before randomization, results up to 4 weeks old are acceptable

⁹ 12- lead ECG: within 30 min after IMP administration

¹⁰ Respiration: blood gas analysis (oxygenation index, blood lactic acid) or pulse oximetry.

¹¹ Immune function: immunoglobulin (Ig A, Ig M, Ig G)

¹² Biomarkers comprising (per collection of whole blood 10-12 ml)

1 Li-Heparin blood collection tube (5-6 ml):

1. Plasma equilibrium angiotensin levels: Angiotensin II (Ang II), Angiotensin 1-7 (Ang. 1 -7), Angiotensin 1-5 (Ang 1-5), Angiotensin I (Ang I), Angiotensin 1-9 (Ang 1-9)
2. Aldosterone
3. ACE2 Activity and ACE2 concentration
4. Other exploratory RAAS Biomarkers indicators: specific exploratory indicators will be determined as needed

1 EDTA blood collection tube (5-6 ml):

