8.5.2.2.9 Assessment of Respiratory Condition

To assess the respiration of the patient a blood gas analysis (oxygenation index, blood lactic acid) or pulse oximetry will be performed (Table 1).

Detailed information is provided in the Investigator Manual.

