8.5.2.2.11 Modified Sequential Organ Failure Assessment (mSOFA) score

The mSOFA score [12] is made up of the following components:

- SpO₂/FiO₂ (mmHg)
- Central Nervous System: Glasgow coma score (GCS)
- Cardiovascular
- Liver
- Platelets
- Renal: Creatinine

Detailed information is provided in the Investigator Manual.

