4.2 Demographics and Other Covariates

Demographic data

Demographic data (Age, Age group (< 65 years/ >= 65 years), Sex, Race, Ethnicity, Body weight, Body height, BMI (Body Mass Index)) will be tabulated and listed.

Other demographic data like history of smoking and alcohol use, if available, will be listed only.

Prior and concomitant medication (CM)

Prior and concomitant medications will be coded by WHO-DD valid version at the end of the study.

Concomitant medications are defined as all medications with stop date >= date of first study medication or ongoing if started before date of first study treatment.

Prior medications include all medications that started and stopped before the date of first study medication. Medications with insufficient date information to determine whether or not they were concomitant will be considered concomitant.

Concomitant medication will be tabulated by anatomical therapeutic chemical (ATC) level 1, ATC level 4, preferred name and listed as well. Prior medication will be listed only.

Comorbidity

Number and percentage of patients with at least one comorbidity (arterial hypertension, diabetes and coronary artery disease) will be shown.

All comorbidity data will be listed as well.

Medical history (MH)

MH events will be tabulated by system organ class and current treatment status (currently treated/ currently not treated). The number of events, as well as the number and rate of affected patients will be reported for each treatment group.

All medical history data will be listed as well.

Respiratory condition (arterial blood gas analysis or pulse oximetry)

Arterial blood pH, PaO₂ and PaCO₂ will be presented using basic statistics of absolute values for all visits and change from baseline for all post-baseline visits.

All respiratory data will be listed as well.

Pregnancy test

The proportion positive or negative pregnancy test results will be tabulated by visit for females with childbearing potential.

All pregnancy test data will be listed as well.

Physical examinations (PEs)

The frequencies of changes (Evaluation (Normal / Abnormal – CS / Abnormal – Not CS)) in PEs (all body systems) since baseline will be shown for all visits using shift tables.

All physical examination data will be listed as well.

Patient status assessment

Patient status assessment will be presented using frequency tables.

Patient status assessment data will be listed as well.

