Absolute values and absolute change in PaO2/FiO2 ratio over time

The PaO2/FiO2 ratio = PaO2 [mmHg] / FiO2

This will be evaluated on each visit for ventilated patients only. If entries are not changed compared to previous entries, no entry will be done within the eCRF.

If ventilation is ongoing and/or no stop date is available, the PaO2/FiO2 ratio will be considered until date of study completion/ discontinuation or date of death respectively.

Baseline is defined as first observation of PaO2/FiO2 ratio (individual start value). Basic statistics for the PaO2/FiO2 ratio for both the absolute values and the absolute change from baseline will be tabulated by day of ventilation. Daily means will be used when more than one assessment is available per day.

Absolute values and absolute change in notified sequential organ failure assessment score (mSOFA score) over time

The mSOFA score was introduced with protocol version 5.0 and is available for patients who are included with protocol version 5.0 and higher. For patients who are included with previous protocol versions (protocol version 4.0 and lower), mSOFA score is available from the time when protocol is in effect at the centers.

Basic statistics for the mSOFA score for both the absolute values and the absolute change from baseline will be tabulated by visit.

SOFA score (protocol version 4.0 and lower) will be listed only.

Time to a 2-point decrease in WHO's 11-Point Score system

Time to 2-point decrease [days] = Assessment date of first ≥ 2 improvement - Date of randomization.

Patients without documented 2-point decrease who completed the study or was early terminated or discharged from hospital before Day 28 will be censored at the date of last WHO assessment available.

Time to 2-point decrease will be analyzed using Kaplan-Meier estimates and plots, log-rank test, and Cox proportional hazards model (adjusted for center and age to derive hazard ratios and corresponding 95% confidence intervals).

Kaplan-Meier estimates and Log-rank test

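### PaO2/FiO2 is promised at every visit, but the schedule does not require a PaO2 and the SAP keeps only ventilated patients, so the by-arm table is not a randomised comparison

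*Protocol*

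**What the plan says.** **Definition.** Protocol Synopsis, secondary endpoint 8: "The PF ratio is defined as PaO₂ [mmHg] divided by FiO₂ [%] and will be evaluated on each visit". Section 8.7.1.2.5 repeats this. Absolute values and change from baseline (Day 1) are to be tabulated, and no patient group is singled out.

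**Schedule.** Table 1 lists the respiratory assessment from Screening to Day 28. Footnote 10 describes it as "blood gas analysis (oxygenation index, blood lactic acid) or pulse oximetry". Section 8.5.2.2.9 says the same: "a blood gas analysis (oxygenation index, blood lactic acid) or pulse oximetry will be performed". Neither says when a blood gas is needed; 8.5.2.2.9 refers to the Investigator Manual for detail.

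**SAP treatment of the ratio.** SAP 4.4.2 evaluates the ratio only while a patient is ventilated, defines baseline as the patient's first available ratio, and tabulates by day of ventilation. SAP section 5 lists two changes from protocol (wording of the WHO scale and coding of age), and this is not one of them. SAP 4.7 plans no imputation.

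**Other oxygenation outputs.** SAP 4.2 says arterial pH, PaO2 and PaCO2 "will be presented using basic statistics of absolute values for all visits and change from baseline for all post-baseline visits". SAP 4.5 summarises oxygen saturation at all visits. Protocol 8.5.2.2.11 makes SpO2/FiO2 a component of mSOFA, but the SAP reports the total score: "Basic statistics for the mSOFA score for both the absolute values and the absolute change from baseline will be tabulated by visit".

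**The concern.** The endpoint needs an arterial PaO2 that a fully compliant site need never record, at baseline or later. The protocol (8.7.1.2.4) expects very few missing values, yet here the schedule itself permits them. The SAP then confines the ratio to ventilated patients. Randomisation balances the arms as allocated; it does not balance those who later come to be ventilated. If invasive ventilation is meant, that subset is defined by a component of the primary endpoint.

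If the drug affects who is ventilated, the two columns of the table describe differently selected patients, and a difference between them, or its absence, cannot be attributed to treatment. No planned table relates oxygenation to FiO2 across the FAS.

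**Working it through.** **1. Protocol and SAP side by side**

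| Item | Protocol | SAP 4.4.2 |
|---|---|---|
| Patients | no restriction | ventilated only |
| Baseline | Day 1 | first ratio recorded |
| Time axis | visit | day of ventilation |
| PaO2 required? | no, oximetry accepted | not addressed |

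The SAP table is thus a different analysis from the protocol's.

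**2. The plan's own figures.** The documents give no N, SD or power for this endpoint. The one design calculation, for the primary endpoint, reproduces: with 50% vs 30%, two-sided 5% and 80% power,

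n = [1.960·√(2×0.4×0.6) + 0.842·√(0.25+0.21)]² / 0.20² = (1.358 + 0.571)² / 0.04 ≈ 93 per group.

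It matters here only as a source of planned event rates.

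**3. How many patients the ventilated-only rule could leave out.** Take 100 per arm and the planned 50% and 30% composite rates, and *assume* that a share f of events involves invasive ventilation.

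| f | Ventilated, placebo vs APN01 | Of 200 without a ratio |
|---|---|---|
| 1 | 50 vs 30 | 120 (60%) |
| 0.75 | 37.5 vs 22.5 | 140 (70%) |
| 0.5 | 25 vs 15 | 160 (80%) |

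Fewer would be left out if ventilated includes non-invasive support, which this part of the SAP does not define.

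**4. What conditioning on ventilation can do.** *Assume* a normal latent severity, one fixed ventilation threshold and f = 1.

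- Shift that turns 50% into 30%: 0 − Φ⁻¹(0.3) = 0.524 SD.
- Mean severity among ventilated placebo patients: φ(0)/0.5 = 0.798.
- Among ventilated APN01 patients: −0.524 + φ(0.524)/0.3 = −0.524 + 1.159 = 0.635.
- Difference seen: 0.798 − 0.635 = 0.163 SD, against a true 0.524 SD.

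This shows the mechanism and is not a forecast.

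**5. What optional blood gases could do if all patients were tabulated, as the protocol reads.** *Assume* a normal P/F with SD 80 and arm means 180 vs 210 or 200 vs 230, limited to 50–476. The probability w of a blood gas depends on whether P/F is <150, 150–250 or >250. The observed arm mean is ∫x·w(x)f(x)dx / ∫w(x)f(x)dx. Limits are applied either by clipping values to the bounds (true differences 28.9 and 29.4) or by truncation (25.3 and 26.7). Cells show the observed difference and the loss, for the two pairs of means in order.

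| w by band | Clipped | Truncated |
|---|---|---|
| 0.9, 0.5, 0.15 | 22.1 (23.6%); 23.5 (19.9%) | 18.6 (26.4%); 20.7 (22.4%) |
| 0.8, 0.5, 0.3 | 26.6 (8.1%); 28.4 (3.3%) | 22.9 (9.5%); 25.4 (4.7%) |
| 1, 0.3, 0.05 | 18.1 (37.3%); 19.8 (32.7%) | 15.0 (40.8%); 17.1 (36.0%) |
| 0.7, 0.5, 0.4 | 28.6 (1.2%); 30.0 (−2.1%) | 24.9 (1.9%); 27.0 (−1.3%) |

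The loss runs from about zero, with a change of sign, to about 40%. It is set by the assumed w, which the documents do not give.

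**The case against.** A reader might infer that oxygenation is measured only in the sickest patients. The documents do not support that. Oxygen saturation is a vital sign at every visit and is summarised for all visits (SAP 4.5). Total mSOFA and the WHO score also partly capture oxygen support. Only the ratio is restricted.

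A reader might also infer that blood gases go to deteriorating patients and that a true benefit is therefore understated by a known amount. That is plausible but unstated: no section says when a blood gas is taken, and the Investigator Manual is not available. The mildest gradient in step 5 gives essentially no bias. Step 5 also describes the protocol's table, not the ventilated-only table that the SAP will produce.

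Further, mSOFA is not a perfect substitute. SAP 4.4.2 says it began with protocol version 5.0, and earlier patients have it only from when that version took effect at their center. Table 1 lets a Day 28 phone visit omit it. Nothing visible shows that FiO2 is stored for non-ventilated patients. Annex 1 uses SpO2/FiO2 only as a cutoff when pO2 is missing, which is weak precedent for a continuous measure.

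All of this stands, and it limits the claim and the fix. It does not remove the mismatch between definition, schedule and SAP. Nor does the saturation table fill the gap: inclusion criterion 3 accepts 93% or less on room air or on oxygen, so saturation alone cannot separate those states.

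**Conclusion.** The point holds in limited form. The protocol's endpoint, its schedule and the SAP disagree on who has a P/F ratio, from what baseline and on what time axis, and the SAP's restriction is undeclared. The resulting subset forms largely after randomisation (the SAP allows for some ventilation starting earlier) and may differ by arm, so the table cannot be read as a randomised comparison.

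The size and direction of any bias are unknown. The range of about 0 to 40% rests wholly on assumed blood-gas probabilities, and the 60–80% without a ratio on assumed shares of invasive ventilation. This is one of 16 secondary endpoints, planned as summary statistics without a test. The primary test and the sample size do not depend on it.

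**What to change.** In SAP 4.4.2:

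- Add SpO2/FiO2 by visit, with change from the pre-dose value, for all FAS patients who have it. Give the arm difference with a 95% CI, adjusted for baseline.
- Show numbers assessed, discharged and dead by arm and visit, since this measure too is seen only in those assessed. It is less selected, not free of selection.
- Keep PaO2/FiO2 as a supplementary table labelled as a post-randomisation subset, with the number of patients with a PaO2 by arm and visit. Define ventilated, and give the unit of FiO2: the protocol uses percent and the SAP states none, a factor of 100 if taken literally.

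In SAP section 5, declare the ventilated-only restriction, the changed baseline and the changed time axis.

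State the limits: mSOFA only from protocol version 5.0, possible omission at Day 28 phone visits, and less information from SpO2/FiO2 at high saturation.

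The cost is SAP wording, one derived variable and one table of counts, provided the sponsor confirms that SpO2 and FiO2 are stored for non-ventilated patients. If they are not, the labelling, counts and declaration can still be done at almost no cost, but the FAS summary cannot.

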1 STUDY SCHEME

2 STUDY SCHEDULES

Table 1:

Procedures and assessments	Screening period	Treatment period ²⁰							Follow up period		
	Day -1*	Day 1	Day 2	Day 3	Day 4	Day 5	Day 6	Day 7	Day 10 (±1 day) ¹⁶	Day 14 (± 1 day) ¹⁶	Day 28 End of Study Visit (or early termination visit) (± 1 day) ¹⁵
Informed consent	X										
Inclusion and exclusion criteria	X	X ※**									
Demographics ¹	X										
Medical history ²	X										
Randomization*		X ※*									
Treatment		X ¹⁴	X	X	X	X	X	X			
Score Assessment of WHO's 11-point scale	X	X ※**	X	X	X	X	X	X	X	X	X ¹⁹
PCR (quantitative or qualitative) ³	X	X ※**		X		X		X		X	X ¹⁷
Vital signs ⁴	X	X ※	X	X	X	X	X	X	X	X	X ^{17, 18, 19}
Physical examination ⁵	X	X ※**	X	X	X	X	X	X	X	X	X ^{17, 19}
Serum or urine pregnancy test ⁶	X										X ^{17, 19}
Clinical laboratory assessments ⁷	X	X ※**	X	X		X		X	X	X	X ^{17, 19}

	Screening period	Treatment period ²⁰							Follow up period		
Procedures and assessments	Day -1*	Day 1	Day 2	Day 3	Day 4	Day 5	Day 6	Day 7	Day 10 (±1 day) ¹⁶	Day 14 (± 1 day) ¹⁶	Day 28 End of Study Visit (or early termination visit) (± 1 day) ¹⁵
HIV/HBV/HCV Serology ⁸	X										
ECG ⁹	X	X ※**	X	X		X		X	X	X	X ^{17, 19}
Assessment of Respiratory condition ¹⁰	X	X ※**	X	X	X	X	X	X	X	X	X ¹⁷
mSOFA score	X	X ※**	X	X	X	X	X	X	X	X	X ¹⁷
Assessment of Immune function ¹¹		X ※**	X	X		X		X	X	X	X ^{17, 19}
Biomarker ¹²		X ※		X		X		X		X	X ^{17, 19}
Patient status assessment ¹³			X	X	X	X	X	X	X	X	X ¹⁷
Adverse Events		X	X	X	X	X	X	X	X	X	X
Concomitant Medication		X	X	X	X	X	X	X	X	X	X

* In case the required screening procedures take less time, randomization and start of treatment could be performed also on the same day then screening. The time period between start of screening procedures and start of treatment must not exceed 24 hours.

** Events do not need to be done if randomization is on the same day as Screening

※: prior dosing

mSOFA score: modified Sequential Organ Failure Estimated Score

¹ Demographic data: gender, age, ethnicity, height, history of allergies, history of smoking and alcohol use, weight, body mass index.

² Medical history: Medical history for the least 4 weeks.

³ If PCR was performed within 5 days before the screening visit, the test does not need to be repeated at screening and the available test results can be used.

⁴ Vital signs include temperature, heart rate, respiration, blood pressure, and oxygen saturation. Vital signs need to be tested before and after each dose (within 30 min before/after IMP administration).

⁵ physical examination could also be documented in the context of the general visit/health status assessment e.g. during a general clinical review

⁶ Pregnancy Test: for FOCP only

⁷ Laboratory tests include the following: in case a local lab cannot perform any of these parameters it should be reported as missing value

- Inflammatory indicators: C- reactive protein (CRP), erythrocyte sedimentation rate (ESR), and procalcitonin.
- Blood routines include: red blood cell (RBC) count, hematocrit (HCT) or hematocrit total, and classification of white blood cells (WBC), hemoglobin (Hb), platelet (PLT) count.
- Urine routine includes: glucose (GLU), pH (PH), urinary protein (PRO), red blood cells (BLD), and white blood cells (LEU).
- Stool routine + occult blood: red blood cells (BLD), white blood cells (LEU), occult blood.
- Blood biochemistry includes: aspartate aminotransferase (AST), alanine aminotransferase (ALT), alkaline phosphatase (AKP), total bilirubin (TBI), total protein (ALB), albumin (ALB), urea nitrogen (BUN), Creatinine (Cr), uric acid (UA), potassium (K), sodium (Na), eGFR (assessment is calculated according to the formula used in local laboratory).
- Myocardial enzymes: creatine kinase (CK) and isoenzyme (CKMB), lactate dehydrogenase (of LDH), [alpha] - hydroxybutyrate dehydrogenase ([alpha] - HBD), troponin (of cTnI).
- Coagulation functions include: prothrombin time (PT), activated partial thromboplastin time (APTT), D- dimer, FIB

⁸ results do not need to be available before randomization, results up to 4 weeks old are acceptable

⁹ 12- lead ECG: within 30 min after IMP administration

¹⁰ Respiration: blood gas analysis (oxygenation index, blood lactic acid) or pulse oximetry.

¹¹ Immune function: immunoglobulin (Ig A, Ig M, Ig G)

¹² Biomarkers comprising (per collection of whole blood 10-12 ml)

1 Li-Heparin blood collection tube (5-6 ml):

1. Plasma equilibrium angiotensin levels: Angiotensin II (Ang II), Angiotensin 1-7 (Ang. 1 -7), Angiotensin 1-5 (Ang 1-5), Angiotensin I (Ang I), Angiotensin 1-9 (Ang 1-9)
2. Aldosterone
3. ACE2 Activity and ACE2 concentration
4. Other exploratory RAAS Biomarkers indicators: specific exploratory indicators will be determined as needed

1 EDTA blood collection tube (5-6 ml):

1. Plasma-Renin-Concentration (PRC)
2. Cytokines: interleukin- 6 (IL-6), interleukin- 8 (IL-8), soluble tumor necrosis factor receptor II (sTNFrII), PAI-1, vWF, tumor necrosis factor - α
3. Alveolar epithelial markers: soluble advanced glycation product receptor (sRAGE), surface-active protein- D (SP-D)
4. endothelial markers: angiopoietin -2 (Angiopoietin-2)
- 5.
6. COVID-19 antibodies, viral load

¹³ Patient status assessments includes: no change, discharge from hospital, transition to critical illness, and death.

¹⁴ 1st dosing could also be on the evening of Day -1 in case randomization is on the same day as screening.

¹⁵ Follow-up Visits (Day 28) may be performed as phone visit or in-home visit where applicable. .

¹⁶ If a patient is already discharged from the hospital, the follow-up visits could be performed on an out-patient basis or at patient's home provided the patient agrees to that.

¹⁷ Assessments do not have to be performed in case of a phone visit

¹⁸ Targeted Physical examination by phone interview

¹⁹ The following assessments will be performed during in home-visits (Clinical Laboratory assessment, ECG, Assessment of immune function and Biomarker, if possible)

²⁰ If a patient will be discharged from hospital before day 7 treatment can be stopped at day of discharge.

